The following events are considered protocol-defined AEs and should be recorded on the AE log:

1. Weight gain: 5% increase compared to baseline
2. Increased blood pressure: increase of >20mm systolic or 10mm diastolic compared to baseline
3. Increased A1c: absolute increase of 1% or greater from baseline (Screening visit value) that is sustained across 2 consecutive measures
4. Hypokalemia: any potassium value below the lower limit of normal
5. New Osteopenia (compared to Baseline): DEXA T score between -1 and -2.5
6. Osteoporosis: DEXA T score less than -2.5
7. A DEXA T score drop of ≥ -0.5 during the study

As is typical, the study will not be powered based on safety and tolerability measures because AEs are anticipated to be rare and because the type and severity of AEs may be unpredictable. **The main secondary endpoint for safety and tolerability will be a comparison of the number of serious adverse events (SAE) over the study period in the ACTH group versus the placebo group.** A SAE will be considered any event with a score equal or greater than 3 on the Common Terminology Criteria for Adverse Events (CTCAE) version 4.03. AEs receiving a mild or moderate grade will also be compared between the two treatment groups.

C. Cognition

Cognitive dysfunction is ubiquitous in MS, affecting an estimated 40-70% of patients (33), and is a major cause of disruption in daily and occupational function in MS patients (34). The most common domains of cognitive impairment in MS are memory, processing speed, visuospatial functions, verbal abilities, sustained attention and

executive function (35). The BRB-N is a set of five cognitive tests developed by National MS Society's Cognitive Function Study Group as a research tool to detect cognitive changes in MS patients and to evaluate the effect of treatment interventions on cognition (36). The five neuropsychological tests comprising the BRB-N were chosen for their ability to assess the cognitive domains most frequently impaired in MS in a practical time period (20-30 minutes). The BRB-N includes the Selective Reminding Test (SRT, a test of verbal learning and delayed recall), the 10/36 Spatial Recall Test (10/36, visuospatial learning and delayed recall), the Symbol Digit Modalities Test (SDMT, sustained attention and processing speed), the Paced Auditory Serial Addition Test (PASAT, sustained attention and processing speed) and Word List Generation task (WLG, verbal fluency).

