2. Extrapolated to a 3 year follow up period, 60% of progressive MS patients will show a 20% or greater increase in T25FW.

Utilizing a significance level of 0.05 and equal sample sizes, 42 subjects per treatment arm would provide 80% power to detect a 50% difference in the proportion of subjects reaching the threshold of 20% worsening in T25FW ($P1 = 0.6$, $P2 = 0.3$, $\alpha = 0.05$, $\beta = 0.2$, 2-sided test). Given the length of the study, we anticipate a dropout rate of up to 10-20% of randomized subjects. To account for this possibility, a total sample size of 100 subjects (50 per treatment arm) will be randomized.

C. Randomization

The study will utilize blocked randomization stratified by study center, with equal (1:1) allocation to the ACTH and control groups.

D. Blinding

Study subjects, their referring physicians, the study monitor, and all study personnel who come in contact with study subjects (including site principal investigators, examining neurologists, study coordinators, nurses, and other study staff and their designated backups) will be blinded to treatment allocation. One investigator who will not come in direct contact with study subjects ([name]) as well as the study statistician and other members of the Data Safety Monitoring Board (DSMB, see section 7F) will be unblinded, to allow for assessment of any safety concerns that may arise over the course of the study.

E. Data Analysis Plan

Descriptive analyses of baseline characteristics and all outcome measures (primary and secondary) will include means with standard deviations or medians with ranges for continuous variables depending on the parametric or non-parametric distribution of the variables, and frequencies with percentages for categorical variables. Between group (ACTH and placebo) comparisons of baseline characteristics and baseline outcome measures will be done using two sample t-tests or Wilcoxon rank sum tests for parametric and non-parametric continuous variables, respectively, and Chi-square tests or Fisher's exact tests for categorical variables.

Models will adjust for age, gender, and MS phenotype; EDSS and disease duration will be included as covariates if significant in preliminary models. Interactions between treatment group and MS phenotype will be tested in each model; if significant, treatment effect will be evaluated in models stratified by MS phenotype.

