The possibility of mid-study therapy regimen change for some subjects (see Exclusion criteria g. and h.) will be accounted for in analysis by running models with and without these subjects to explore the impact of these changes on analysis results. If results from the two models are consistent, all subjects will be included in the final model.

There are multiple distinct outcomes of interest in this study; since each outcome measures a unique aspect of MS progression no adjustment for multiple comparisons is planned.

Primary endpoint:

Between group differences in the odds of a 20% or greater increase in T25FW, the primary outcome measure of clinical progression of MS, will be tested at 36 months using multiple logistic regression models adjusted for covariates. Generalized

estimating equation (GEE) models will be used to test for between group differences in change over time in clinical progression (20% or greater increase in T25FW) adjusted for covariates. To test for between group differences in time to clinical progression distribution curves, Cox proportional hazards models (conditional on model assumptions being met) or Kaplan-Meier analysis will be used.

Secondary endpoints:

Safety and tolerability

To evaluate safety and tolerability of ACTH, lists and descriptive statistics of adverse events, serious adverse event, and treatment compliance will be compiled and calculated for each group at each visit. Fisher's exact tests will be used to test for between group differences in specific adverse event rates, serious adverse event rates, and treatment compliance rates.

Between group differences in mean changes in physical exam and laboratory measures (weight, blood pressure, HgbA1c, bone mineral density) will be tested using two-sample t-tests. In addition, between group differences in the proportion of subjects with abnormal blood pressure, HgbA1C, electrolyte and bone mineral density levels will be tested using Chi-square tests or Fisher's exact tests.

Change in ambulation, cognition, and global measures of MS-related disability scores

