Multiple linear regression models will be used to test for between group differences in LCVA scores adjusted for other covariates. Binocular LCVA scores will be used to test for a treatment effect on vision changes; monocular LCVA scores will be used for correlation with OCT measures (from the matching eye). Generalized estimating equation (GEE) models will be used to test for between group differences in change over time in vision loss rates adjusted for other covariates. In addition correlation of LCVA with OCT measures (RNFL and macular volume) will be evaluated using Pearson correlation analysis (Spearman correlation will be used if measures have skewed distributions).

Between group differences in mean OCT macular volume scan measures will be tested using multiple linear regression models adjusted for covariates. mixed model analyses of repeated measures will be used to test for between group differences in change over time in OCT macular volume measures.

7. Study Procedures

A. Schedule of study procedures:

1. Symptoms questionnaire for subjective adverse events at baseline, 3, 6 and 12 months and then annually.
2. Comprehensive metabolic panel (CMP) and hemoglobin A1C (HbgA1C) at screening, 6 and 12 months, and then annually.
3. EDSS and DEXA scan (both hips/femurs and lumbar spine) at screening and then annually.
4. OCT at baseline and then annually.
5. MSFC, T25FW, 6MWT, LCVA, MSWS-12, AI, FSS and BRB-N at baseline and then annually.
6. Practice sessions (at screening visit:
 - a. BRB-N - 1 practice session

- b. PASAT - 2 practice sessions (in addition to the one administered during BRB-N)
- c. 9HP - 3 practice sessions

Table 1. Study Schedule

	V1 Screen 0 to -4 wks	V2 Baseline M0	V3 *** M3	V4 M6	V5 M12	V6 M18	V7 M24	V8 M30	V9 M36
Informed Consent	X								
Inclusion/Exclusion	X								
Injection Training		X							
Blood Pressure		X	X	X	X	X	X	X	X
Weight		X	X	X	X	X	X	X	X
Safety Lab Tests^a	X			X	X		X		X
Skin & Edema Assessment		X	X	X	X	X	X	X	X
OCT		X			X		X		X
LCVA		X			X		X		X
EDSS	X				X		X		X
Timed 25-Ft Walk		X			X		X		X
9-Hole Peg Test	XXX	X			X		X		X
PASAT (apart from BRB-N)	XX								
6 Minute Walk Test		X			X		X		X
MS Walking Scale - 12		X			X		X		X
Fatigue Severity Scale (FSS)		X			X		X		X
Hauser Ambulation Index		X			X		X		X
Brief Repeatable Battery	X	X			X		X		X
DEXA Scan^b	X ^c				X		X		X
Randomization		X							
Symptom Questionnaire		X	X	X	X	X	X	X	X
Concomitant Medications		X	X	X	X	X	X	X	X

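### Blood pressure, A1c, potassium and bone safety outcomes ignore treatment started during the trial: the A1c event can be erased, and the other measured-value comparisons are attenuated

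*Combined protocol and SAP*

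**What the plan says.** Section 5.B introduces its list with "The following events are considered protocol-defined AEs and should be recorded on the AE log". The entries for blood pressure, A1c, potassium and bone are each a change in, or a level of, a measured value. Only the A1c entry (item 3) asks for confirmation: the rise of at least 1 point must be one "that is sustained across 2 consecutive measures". The others need a single crossing.

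Section 6.E (Secondary endpoints, Safety and tolerability) plans three kinds of comparison:

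- Fisher's exact tests on rates of specific adverse events and serious adverse events.
- Tests of mean change: "mean changes in physical exam and laboratory measures (weight, blood pressure, HgbA1c, bone mineral density) will be tested using two-sample t-tests".
- Chi-square or Fisher tests on the proportion of subjects with abnormal blood pressure, HgbA1C, electrolytes and bone mineral density.

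Table 1 in section 7.A has a row for "Concomitant Medications" marked at every visit from V2 to V9, but no safety analysis uses it. The only rule in 6.E for therapy changed during the trial refers to exclusion criteria g and h, which concern MS therapies.

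**The concern.** Section 6.B calls safety and tolerability over three years the main objective, and 5.B names glucose intolerance, osteoporosis, hypertension and electrolyte disturbance among the effects of concern. If ACTH causes these, more ACTH subjects will be given a drug for them, and that drug pulls the later study readings back towards normal. A comparison that sees only the readings is then biased towards no difference, which in a safety comparison is the unfavourable direction. The plan recognises the same problem for efficacy, where it reruns models with and without subjects whose MS therapy changed. It has no counterpart for the safety measures.

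**Working it through.** **The plan's own figure.** The only sample-size figure concerns the walking endpoint. With 0.60 v 0.30, two-sided 0.05 and 80% power:

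n = [1.96 × √(2 × 0.45 × 0.55) + 0.8416 × √(0.24 + 0.21)]² / 0.30² = (1.379 + 0.565)² / 0.09 ≈ 42 per arm.

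This reproduces the stated 42. It does not bear on safety, and 5.B says the study is not powered on safety. Only the planned 50 per arm is carried forward.

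**Where treatment can act on each outcome.**

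- *A1c event.* Laboratory tests are at screening and Months 6, 12, 24 and 36. A first rise at Month 6 is confirmed at Month 12 (6 months later), at Month 12 by Month 24 (12 months), and at Month 24 by Month 36 (12 months). If treatment in that gap brings the second value below +1 point, no protocol-defined event is recorded. (Separately, a first rise at Month 36 cannot be confirmed within the schedule.)
- *Blood pressure, potassium and T-score events.* One crossing is enough, and it stays on the log if treated later. An event is lost only if treatment begins before any study reading crosses the limit.
- *Mean-change tests (blood pressure, A1c, bone) and proportion-abnormal tests (these plus electrolytes).* A value measured on treatment enters as if untreated.
- *Weight event.* No corresponding drug class is at issue.

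**Size for the A1c event.** The documents give no rates, so these are assumptions. Let p be the true event rate in an arm and m the share of events masked by treatment and captured by no other route, with m equal in both arms. The recorded rate is p(1 − m). Power is the exact two-sided Fisher power at 0.05 with 50 per arm.

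| True rates | m = 0 | m = 25% | m = 50% |
|---|---|---|---|
| 20% v 5% | 51% | 34% | 16% |
| 30% v 10% | 64% | 45% | 24% |

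At m = 50%, 20% v 5% is recorded as 10% v 2.5%. The risk difference halves, from 15 to 7.5 points, while the ratio stays at 4. The ratio would shrink too if the masked share were larger on ACTH. With rarer events and no masking at all, power is already 19% (10% v 2%), 9% (8% v 2%) or 3% (6% v 2%).

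**Size for blood pressure.** This is a simulation over the seven post-baseline visits, with assumed inputs throughout: true ACTH effect +6 mmHg; usual mean 125 and SD 14; visit-to-visit SD 8; drug-response SD 5; drift SD 6; 50–90% of subjects newly at 140 or more treated, with a fall of 10–15 mmHg.

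| Analysis | Result | Without treatment |
|---|---|---|
| Last-visit mean difference, as observed | 3.9–4.8 mmHg | 6 mmHg |
| Difference in share ever more than 20 mmHg above baseline | 17–19 points | 20.5 points |
| Same, counting a crossing or a drug start | about 21 points | 20.5 points |
| Mean difference using last value before drug start | about 6.6 mmHg | 6 mmHg |

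The last row also produces an apparent placebo rise of 1.4–2.1 mmHg where the true change is zero, because the reading that prompts treatment is selected for being high.

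**The case against.** The strongest reply is that the safety comparison has other routes. Single-crossing events remain on the log. A diagnosis made elsewhere can be volunteered at any follow-up visit or monthly contact, is graded and logged, and can enter the same Fisher tests of adverse event rates. The designated main safety endpoint is the serious adverse event count, not these tests. Comparing values as observed, whatever treatment followed, is also a legitimate treatment-policy comparison. And 5.B expects adverse events to be rare, so 20% or 30% on ACTH may be far too high.

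Much of this stands. A reader might infer that a treated drug effect disappears from the safety comparison, or that all seven protocol-defined events are affected. The documents support neither. The first would need every event to be treated before measurement and reported by no other route. The second fails for weight, and single-crossing events are erased by later treatment in no case.

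What does not stand is the idea that the backstop closes the gap. It depends on the subject reporting the diagnosis. The elicited questionnaire described in 5.B names none of hypertension, diabetes, potassium or bone. Volunteered reports do not enter the mean-change or proportion-abnormal tests. And the A1c definition is a stated rule that can drop precisely the cases that were treated.

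**Conclusion.** The concern holds in a limited form and merits a correction. The A1c event can be erased by treatment between laboratory visits. The mean-change and proportion-abnormal tests are attenuated towards no difference if more ACTH subjects are treated. Single-crossing events are largely preserved: 17–19 of 20.5 points in the blood pressure illustration.

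The magnitude cannot be established from the documents. The fall in Fisher power from 51% to 34–16% assumes A1c rates of 20% v 5%, 50 per arm, a quarter to a half of events masked equally in both arms, and no capture by volunteered report. It is therefore an upper illustration for those rates. At 10% v 2% or rarer, power is low to begin with and the argument rests on the direction of the bias, not on lost power. The blood pressure figures rest wholly on assumed thresholds, treatment shares and responses.

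**What to change.** These are changes to analysis definitions only.

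- **5.B, item 3:** after a first raised value, count a new start or dose increase of a glucose-lowering drug for that indication as meeting the confirmation requirement.
- **6.E, proportion-abnormal tests** (blood pressure, A1c, electrolytes, bone): count a subject as abnormal if the threshold is crossed or a drug for that condition is newly started or increased, taken from the concomitant medication log. Tabulate these starts by arm.
- **6.E, mean-change t-tests:** keep them as observed, and label them as including the effect of any treatment started. Do not substitute the last value before drug start, which overstates the change as shown above.

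The cost is protocol and SAP wording, with no new visits or patients. The indication must be recorded or confirmed (the case report form is not shown, so it may already be), and starts for other reasons must be screened out while treatment allocation is still blinded. That screening should be light for glucose and bone drugs, because diabetes and osteoporosis are exclusions at entry. Hypertension is not an exclusion in its own right, so dose increases matter more for blood pressure.

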A key outcome measure of this phase II study is the safety and tolerability of pulsed ACTH compared to placebo. Little background information on adverse effects of pulsed ACTH in MS is available. A preliminary report of a one-year study (17) reported generally no increase in adverse effects in MS subjects receiving pulsed ACTH compared to pulsed MP, and fewer "psychiatric episodes" in the ACTH group. Potential AEs of concern are primarily those related to corticotropin effects, i.e. common steroid-related AEs such as increased risk of infection, weight gain, glucose intolerance, osteoporosis, hypertension, fluid retention, electrolyte derangements, and mood or behavioral changes.

Safety and tolerability of ACTH will be assessed in three ways: via volunteered responses from subjects regarding AEs, by elicited responses regarding specific symptoms, and by laboratory and physical exam measures. The advantage of volunteered (unsolicited) responses is that they allow unexpected AE's to be assessed and tend to highlight more serious or distressing AEs, while elicited responses have the advantage of more sensitive detection of specific AEs of interest (32). The volunteered responses will be obtained by an investigator or study coordinator at each follow-up visit, asking the

subject "Have you had any medical problems since your last visit?" Responses will be recorded on a log and severity will be rated according to the Common Terminology Criteria for Adverse Events (CTCAE) version 4.03. Subjects may also report AE's by phone, and these will be rated and logged in a similar manner. Study personnel will contact subjects monthly (by phone, email, etc.) around the time of their scheduled study drug injections, to remind them of the injections and to check for any new AE. If a phone-reported AE is deemed serious or possibly serious, an unscheduled visit will be arranged to allow the local investigator to assess the AE more fully (see section 7E, Unscheduled Study Visits). Elicited responses will be assessed through a questionnaire that will explore insomnia, irritability, dyspepsia, injection pain, edema, dysgeusia, fatigue, vision, skin changes, and changes in menstruation.

Physical exam and laboratory measures will include objective measurements of weight, blood pressure, skin changes, edema, myopathy, cataracts, glucose, electrolyte abnormalities, bone mineral density (DEXA) and hepatic toxicity.

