Unsolicited Adverse Events			X	X	X	X	X	X	X
Dispense Study Drug		X	X	X	X	X	X	X	
Return Drug Vials and Logs			X	X	X	X	X	X	X

^a Safety lab tests: comprehensive metabolic panel and hemoglobin A1C.

^b Bilateral hips and lumbar spine

^c DEXA scan may be omitted at the Screening Visit if subject provides results of DEXA scan done within the 3 months prior to the Screening Visit

*** The month 3 visit is primarily a safety visit to assess AEs and to assess any difficulties subjects may be having with study drug injections. No laboratory tests are done, and no physical exam other than the skin and edema assessment (which would be unlikely to yield abnormal findings at 3 months, since chronic steroid side effects would likely take longer to occur in the 3 day per month pulsed dosing). For patients traveling a long distance to the study, this visit might be much more conveniently done by phone.

While the preference is for the month 3 visit to be done on-site, it can (optionally) be done as a phone visit, e.g. for subjects who 1) are inconvenienced by coming in person for this visit, and 2) have prior experience with taking subcutaneous injections. If this option is chosen, then 1) 6 months' worth of study drug (rather than 3) must be given out at the baseline visit, 2) no study drug dispensing or drug return will occur at the month 3 visit, and 3) no skin and edema assessment will be done at the month 3 visit.

B. Treatment Administration:

ACTH (Acthar gel) and placebo will be provided by the funding sponsor and distributed to individual sites. The study medication will be self-administered at a dose of 80 units subcutaneously for 3 consecutive days every month for the duration of the study. The dose will be reduced to 40 units if the full dose cannot be tolerated. Specific training in the injection procedure will be done prior to the initial injection.

C. Study Staff

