Subjects will be asked to contact their study site if they develop new symptoms that are concerning to them. The local study coordinator will record the reported symptoms on the Unsolicited AE Form, which will be reviewed by the local investigator. An unscheduled study visit will occur if the local investigator deems these AEs as potentially serious, possibly related to study medication, and/or requiring in-person assessment. If the reported symptoms are interpreted as mild and/or unrelated to study medication, the subject may be referred to their primary physician or advised to report back by phone with updates about symptom

evolution/resolution. Unscheduled visits will not be routinely performed for suspected MS relapse (see section 7D, Relapses), although they may occur in this situation if the reported symptoms are interpreted as a possible treatment-related AE. Assessments/procedures performed at an unscheduled visit will include all of the assessments done at Visit 3 (see Table 1) with the exception of study drug distribution; any further assessments and/or procedures (e.g. physical examination, other tests, referrals) will be done at the discretion of the local investigator.

F. Early Termination and Intent to Treat

Once subjects are randomized, regardless of if or the length of time they have been on blinded treatment, they will be included in the efficacy (intent to treat) analysis if efficacy data are available (that is, if they have completed at least one annual follow-up visit). Subjects who withdraw (e.g., due to side effects) prior to completing the Month 12 visit will be asked to return the study drug to the site, and to participate in annual phone calls (Months 12 and 24), and to return to the site for the final visit at Month 36. Subjects who withdraw after completing the Month 12 visit will be asked to return the study drug to the site, and to complete the remaining annual study visits (i.e., Month 24 and Month 36) even though they are not receiving drug. Subjects are of course allowed to decline further participation, in which case they would be considered lost-to-follow-up.

G. Data Safety Monitoring

A DSMB will be formed and will consist of one MS specialist, one neurologist familiar with the evaluation and treatment of MS but not otherwise associated with the study, and the study biostatistician. A DSMB chairperson will be chosen from one of the two neurologists on the DMSB.

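### On scheduled tests, the HbA1c adverse-event rule cannot count a rise first seen at Month 36, and a rise first seen at Month 12 or 24 waits a year for confirmation

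*Combined protocol and SAP*

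**What the plan says.** Section 5.B names the steroid-type harms of concern, among them "increased risk of infection, weight gain, glucose intolerance, osteoporosis, hypertension, fluid retention, electrolyte derangements, and mood or behavioral changes". It then lists seven protocol-defined adverse events for the AE log. Item 3, raised HbA1c, requires an "absolute increase of 1% or greater from baseline (Screening visit value) that is sustained across 2 consecutive measures". The weight, blood pressure, potassium and DEXA items state no confirmation requirement.

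Section 7.A, item 2, schedules "Comprehensive metabolic panel (CMP) and hemoglobin A1C (HbgA1C) at screening, 6 and 12 months, and then annually". Table 1 agrees. Its footnote reads "Safety lab tests: comprehensive metabolic panel and hemoglobin A1C", and that row is marked at screening and Months 6, 12, 24 and 36, but not at Months 3, 18 or 30. Month 36 is the last visit. Section 7.B gives study drug for "3 consecutive days every month for the duration of the study".

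Section 6.E compares specific adverse event rates between arms with Fisher's exact test. It also analyses HbA1c in two other ways: "Between group differences in mean changes in physical exam and laboratory measures (weight, blood pressure, HgbA1c, bone mineral density) will be tested", and the "proportion of subjects with abnormal blood pressure, HgbA1C, electrolyte and bone mineral density levels will be tested". Neither of these carries a two-measure rule.

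The protocol plans no confirmatory repeat test and does not say how to classify a first raised value at the last visit.

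**The concern.** The two-measure rule and the test schedule do not fit together late in the study. A confirmation rule needs a later measurement, and none is scheduled after Month 36. From Month 12 on, the interval to the next measurement is a year.

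Section 6.B gives the main objective as safety and tolerability over three years, and glucose intolerance is a named concern. An effect that builds up with repeated pulses would tend to appear late, where this rule is least able to count it.

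The year-long wait matters for a second reason. Under section 7.F, subjects who withdraw after Month 12 are asked to complete the remaining annual visits off drug. A rise first seen at Month 24 may then be confirmed or refuted by an off-drug value at Month 36. At stake is the HbA1c line in the specific-event comparison of section 6.E.

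**Working it through.** The plan states no figure for this item, so there is none to reproduce. The check is on the schedule.

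**Inputs.** Post-baseline HbA1c tests at Months 6, 12, 24 and 36 (7.A, Table 1). Treatment lasts 36 months (7.B, Table 1). An event requires a raised value at two consecutive measures (5.B, item 3).

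**Step 1: onset window, first test and confirming test**, for a rise that persists:

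| Onset (months) | First seen | Confirming test | Wait |
|---|---|---|---|
| 0–6 | M6 | M12 | 6 months |
| 6–12 | M12 | M24 | 12 months |
| 12–24 | M24 | M36 | 12 months |
| 24–36 | M36 | none | cannot qualify |

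**Step 2: size of the uncountable window.** (36 − 24) / 36 = 12/36 = 33% of treatment time. This equals the share of events lost only if onset is uniform over the 36 months and rises persist. The documents give no onset distribution.

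**Step 3: all patterns.** Four tests, each raised or not, give 2^4 = 16 patterns, of which 15 contain at least one raised value. Eight of the 15 meet the rule. The seven that fail, in the order M6, M12, M24, M36 (1 = raised), are 0001, 0010, 0100, 0101, 1000, 1001 and 1010. The last six include a return below the threshold at the next scheduled test, so excluding them is what a confirmation rule is meant to do. Pattern 0001 differs: it fails because no later measure exists, however large the rise.

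**Step 4: early withdrawals.** Subjects who withdraw before Month 12 are asked only for phone calls at Months 12 and 24 and a visit at Month 36 (7.F). They have at most Month 6 and Month 36 values. The protocol does not say whether two values 30 months apart count as consecutive.

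**Step 5: what lost counts do to the comparison.** This is an illustration only, because the documents give no HbA1c event rates. Assume 50 per arm, a two-sided Fisher test at 0.05, and one third of events lost in each arm:

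| True rates (assumed) | Power, all counted | Rates after losing 1/3 | Power |
|---|---|---|---|
| 24% vs 3% | 0.85 | 16% vs 2% | 0.57 |
| 20% vs 5% | 0.51 | 13.3% vs 3.3% | 0.28 |

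The ratio of the rates is unchanged. The absolute difference shrinks by one third, for example from 21 to 14 percentage points in the first row.

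**Step 6: would more tests close the gap?** Adding HbA1c at Month 30, or at Months 18 and 30, would leave (36 − 30) / 36 = 6/36 = 17% uncountable. Any schedule that ends with a single last test leaves some window, so a classification rule is needed in any case.

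**The case against.** The strongest reply is that item 3 is one entry in an added list and does not replace ordinary adverse-event capture. Section 5.B has subjects asked about medical problems at each follow-up visit and contacted monthly, and Table 1 records concomitant medications at every visit from baseline. A reader might infer that an unconfirmed rise is never recorded. The documents do not support that, because nothing bars logging it as an ordinary adverse event. Nothing requires it either.

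Second, tests outside the schedule are possible. At an unscheduled visit "any further assessments and/or procedures (e.g. physical examination, other tests, referrals) will be done at the discretion of the local investigator". A value obtained between Months 24 and 36 could make Month 36 the second measure. This limits the point to scheduled tests. The protocol does not say whether such a value would count.

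Third, a Month 36 rise still enters the mean-change analysis and, if the level is abnormal, the abnormal-proportion analysis. That offset is real but partial. Section 6.E does not define abnormal HbA1c. Entrants are below 6.5% (section 4, exclusion b), so a rise from 5.3% to 6.3% meets the 1% criterion but might not be classed as abnormal. A mean can also dilute rises confined to a minority.

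Fourth, a reader might infer that the comparison is biased in favour of ACTH. Both arms share the rule and the schedule. Equal proportional loss shrinks the difference and costs sensitivity but does not by itself distort the ratio. Differential loss would need arm-specific patterns of onset, stopping or treatment that the documents do not give.

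Fifth, a reader might infer that the DSMB cannot see glucose harm. On scheduled tests no subject can meet item 3 before their own Month 12 test. However, section 7.G gives the DSMB safety data, not only the AE log, and section 6.D leaves its members unblinded.

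Finally, confirmation trades sensitivity for specificity and may be deliberate. That is a fair reason to keep a confirmed count, but it does not explain leaving a first rise at the last visit unclassified.

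**Conclusion.** The point holds as a limited defect in one event definition. On scheduled tests, a first HbA1c rise at Month 36 cannot be a protocol-defined event, and onset in 12 of 36 treatment months is uncountable. A rise first seen at Month 12 or 24 depends on a value 12 months later, possibly taken off drug. The consequence is under-counting of late events and lower sensitivity of this specific-event comparison, with partial offsets elsewhere in the plan.

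The schedule finding needs no assumptions beyond the planned visits. Reading 12 of 36 months as one third of events assumes uniform onset and persistence. The power figures assume event rates as well.

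A reader might go further and put the loss at one half, by supposing that half of the rises first seen at Month 24 have reversed by Month 36 (1/3 + 1/6). The documents give no recovery rate. The same supposition would apply equally to rises first seen at Month 12, so that figure should not be used. The main safety endpoint, the count of events of CTCAE grade 3 or above, is not defined by this rule.

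**What to change.** In section 5.B, item 3, record the event at the first HbA1c at least 1% (absolute) above the screening value. Add a flag with three levels: *confirmed*, *not confirmed*, *no later measure*. In section 6.E, report first-occurrence and confirmed counts by arm. The same sentence should say whether an unscheduled value can serve as the second measure, and how values separated by missed tests are treated.

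A first rise at Month 36 is then counted and flagged *no later measure*, so the unclassified window falls from 12 of 36 months to 0. The confirmed count keeps the specificity that the present rule was written for.

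The cost is a short edit to 5.B, one case report form field and one extra line in the adverse-event table. No blood draw or visit is added. The downside is small: some isolated rises will be logged in both arms, and the flag lets the reader separate them.
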